4.7 Success Criteria

4.7.1 Primary Measure of Effectiveness

A subject will be considered a success if a BM is achieved within 3 days of surgery. The primary outcome measure of effectiveness will be determined by the comparative rate of patients achieving BM and evading POI in the MNTX group versus placebo.

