3.2 Primary / Secondary Outcomes

The primary outcome will be the time from the end of surgery to the first bowel movement (BM; in hours). A sample size of 43 randomly assigned patients per study group (86 subjects in total) was calculated to detect a treatment effect of MNTX (90% power; alpha = 0.05). This calculation was performed with the assumption that subjects who experience their first BM by day three comprise 50% in the placebo group and 85% in the treatment group. A 10% lost-to-follow up rate was also included in the calculation. The secondary outcomes will be the time to discharge and the time to discharge eligibility (in hours). Finally, exploratory outcomes will include the amount of daily narcotics (in morphine milli-equivalents) administered during the first 4 days or up to hospital discharge. Administration of drug/placebo will be stopped should the patient experience frequent stools, defined as greater than 3 BMs per day.

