4.3 Perioperative and Postoperative Management

Enrolled patients will be given MNTX (0.15 mg/kg rounded to 8 mg or 12 mg) or placebo prior to surgery in the pre-operative holding area and every 24 hours for 3 days following surgery (a total of 4 doses). This dosing matches the FDA approved dosing for the use of MNTX in patients effected by opioid induced constipation.

Following surgery patients' BMs will be closely monitored and the time to first BM will be recorded in hours. Patients will receive routine post-operative orders including early mobilization with a physical therapist on the first post-operative morning, intravenous patient controlled anesthesia for 1-2 days transitioned thereafter to an oral opioid regimen, as well as a bowel routine comprising Docusate Sodium, Senna Glycoside, Polyethylene Glycol 3350, and Bisacodyl

suppositories (started on post-operative day 2, if needed). All patients are also routinely discharged on a tapering oral opioid regimen.

Administration of drug/placebo will be stopped should the patient experience frequent stools, defined as greater than 3 BMs per day. If a treating physician chooses to prescribe the off-label use of Methylnaltrexone for the management of post-operative ileus, the subject will be unenrolled from the study. Abdominal X-rays and CT will be collected and analyzed only if performed as standard of care to evaluate the GI tract following surgery. Additional review of concomitant medications, patient-reported pain levels (NRS), and adverse/serious adverse events will be reviewed daily for up to 96 hours following surgery and at 30 days post-operatively.

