4.8 Subject Withdrawal

It is recognized that the subject's participation in this trial is entirely voluntary, and that she/he may refuse to participate and may withdraw from participation at any time without jeopardy to any future medical care. It is also recognized that the investigator, at his/her discretion, may withdraw a subject from this study based upon his/her professional judgment.

Other Conditions for Withdrawal:

Any subject who develops a severe concurrent medical illness during the trial should be withdrawn. This type of illness is defined as any illness that would hinder the subject's ability to return for scheduled follow-up appointments. Such a withdrawal will not be counted for the purposes of determining success or failure.

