5 STATISTICAL ANALYSIS PLAN

Efficacy analyses will be based on a modified intent-to-treat population including all subjects randomly assigned and having received at least one dose of study drug. The distribution of the primary efficacy end point time of first BM will be estimated via the Kaplan-Meier product-limit method and compared between treatment groups using the log-rank test. Secondary efficacy end points will be evaluated at the $\alpha = 0.05$ level of significance without adjustment for multiple comparisons.

This study will attempt to identify not just relevant demographic and clinical risk factors for POI following spinal fusion, but also will quantify peri-operative opioid use in this patient population in order to determine whether an increased use of opioids increases the risk of POI.

Finally, safety will be assessed by monitoring adverse events (AEs), concomitant medications, vital signs, physical examination findings, ECG findings, and laboratory test results. Withdrawals owing to AEs will be evaluated as a safety end point. Treatment-emergent AEs, potentially clinically important laboratory measurements, and premature study discontinuations will be compared between groups by use of the Fisher exact probability test.

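### Section 4.7.1 makes the primary measure a rate of bowel movement without ileus, Sections 3.2 and 5 make it time to first bowel movement, and no text ranks the two

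*Combined protocol and SAP*

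**What the plan says.** Two different variables are called primary.

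- **Time to event.** Section 3.2: "The primary outcome will be the time from the end of surgery to the first bowel movement (BM; in hours"). Section 5 refers to "the primary efficacy end point time of first BM", estimates it by Kaplan-Meier, and has it "compared between treatment groups using the log-rank test". Section 4.3 supports this reading: "the time to first BM will be recorded in hours". The log-rank test is named only in Section 5.
- **Rate.** Section 4.7.1 first defines success for one patient: "A subject will be considered a success if a BM is achieved within 3 days of surgery". Its next sentence makes the "primary outcome measure of effectiveness will be determined by the comparative rate of patients achieving BM and evading POI in the MNTX group", compared with placebo. That second sentence gives no time window of its own and adds the condition of avoiding POI.

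Section 4.8 uses the success/failure status again. It says "Any subject who develops a severe concurrent medical illness during the trial should be withdrawn", and then: "Such a withdrawal will not be counted for the purposes of determining success or failure". Section 5 bases efficacy analyses on everyone randomized who received at least one dose.

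The sample-size text (Sections 3.2 and 4.2) assumes that 50% on placebo and 85% on methylnaltrexone have a first BM by day three. It asks for 90% power at alpha 0.05, allows 10% loss, and arrives at 43 per arm. It names no test.

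**The concern.** A plan should leave one answer to the question of which result decides the trial. Here one section points to a log-rank comparison of times and another to a comparison of rates. No text calls one of them supportive, calls them co-primary, or says which section governs. A trial that met one criterion and missed the other could be reported either way after unblinding.

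The rate is also incomplete as a criterion. It has no test. Section 2.1 describes POI only as background, without criteria, time window or assessor, and Section 4.3 collects abdominal imaging only when it is done as standard of care. Two people could therefore score the same patient differently. The rate also carries the Section 4.8 exclusion for severe concurrent illness, which does not match the Section 5 population.

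**Working it through.** **Inputs from the documents.** 3-day rates 50% and 85%, power 90%, alpha 0.05, loss 10%, 43 per arm (Sections 3.2 and 4.2).

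**Assumptions not in the documents.** Two-sided tests, exponential times (hence proportional hazards), three days read as 72 h, BM follow-up ending at 72 h, no losses in the simulations, and the rate taken as BM by 72 h without the POI condition. Where 39 per arm is used, it is 43 x 0.90 = 38.7, rounded.

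**1. Does the sample size show which endpoint was meant?**

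- Log-rank (Freedman): HR = ln(0.15)/ln(0.50) = 2.737. Events = (1.960 + 1.282)² x (3.737/1.737)² = 48.6. Per arm 48.6/(0.50 + 0.85) = 36.03, so 37. With loss 37/0.90 = 41.1, so 42.
- Two proportions, pooled: [1.960 x √(2 x 0.675 x 0.325) + 1.282 x √(0.25 + 0.1275)]²/0.35² = 35.5, so 36. With loss 36/0.90 = 40.
- Two proportions, continuity-corrected: 42 before loss, 47 after.

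None gives exactly 43. The Freedman figure is nearest once loss is included, but this does not prove which formula was used. The sample size does not settle the conflict.

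**2. Power at 50% vs 85%.** Expected events by 72 h are 38.7 x 1.35 = 52.2 with 10% removed, or 43 x 1.35 = 58.1 with none removed.

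| Test | about 39 per arm | 43 per arm |
|---|---|---|
| Log-rank, simulated | 95.3% | 96.9% |
| Log-rank, Schoenfeld | 95.3% | 97.0% |
| Log-rank, Freedman | 91.9% | 94.3% |
| Rate, uncorrected chi-square, exact | 93.2% | 95.2% |
| Rate, Fisher, exact | 88.7% | 92.4% |

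**3. False-positive rate if either test may decide.** Simulated with no treatment effect. The lower figure pairs the log-rank test with Fisher, the upper with uncorrected chi-square.

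| Common 3-day rate | 39 per arm | 43 per arm |
|---|---|---|
| 50% | 5.2-6.1% | 4.9-5.7% |
| 67.5% | 5.5-6.9% | 5.6-6.7% |

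Two independent tests would give 1 - 0.95² = 9.75%. The actual figures are much lower because both tests use largely the same events.

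**4. How often the criteria disagree at 50% vs 85%.**

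| Test of the rate | 39 per arm | 43 per arm |
|---|---|---|
| Fisher | 6.8% | 4.9% |
| Uncorrected chi-square | 3.6% | 2.7% |

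With Fisher at 39 per arm, 6.6% of trials have the log-rank test alone significant and 0.2% the rate alone. With chi-square the rate alone is significant in 0.7% (39 per arm) and 0.5% (43 per arm). This leaves 3.6 - 0.7 = 2.9% and 2.7 - 0.5 = 2.2% with the log-rank test alone significant, about four in five of the disagreements.

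**5. The criterion as written.** None of these figures includes the POI condition. The documents give neither a case definition nor an assumed POI rate for this trial, so its effect cannot be computed.

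**The case against.** The strongest reply is that Section 5 already decides the matter. It is the statistical analysis plan, and it names the endpoint, the estimator and the test. Section 3.2 agrees with it, and Section 4.3 collects the data in that form. Section 4.7.1 stands under a heading on success criteria, and its rate has no planned test, so reporting the rate as primary would be a visible departure from Section 5. There is also little to gain by switching, because the rate rarely succeeds where the log-rank test fails.

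Most of this stands. It shows which text should prevail and why the harm is limited. It does not remove a sentence that calls a different quantity the primary outcome measure, and no text subordinates that sentence.

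Three stronger readings are tempting, and the documents do not support them.

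- A reader might infer that the false-positive rate nearly doubles to 9.75%. That figure needs independent tests, and these are strongly correlated.
- A reader might infer from the 3-day proportions that the trial was really sized for the rate. The same proportions lead to 42 per arm through a log-rank formula, closer to 43 than the 40 from pooled proportions.
- A reader might infer that the Section 4.8 exclusion distorts the result. Suppose all of the 10% loss were severe-illness withdrawals, spread evenly over 72 h with 43 per arm. Leaving out those lost before a BM would remove on average 5.0 of 86 patients. The power of the rate test would move from 90.0% to 91.4% (Fisher) or from 93.3% to 93.6% (chi-square).

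**Conclusion.** Wrong as written: the plan states two contradictory primary criteria and no order between them. This is a conflict in operative text, not merely a missing detail.

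The calculable effect is small. The either-test false-positive rate is about 5-7%, and the criteria disagree at the design rates in about 3-7% of trials. The disagreements nearly always favour the log-rank test if the rate is tested by Fisher, and mostly favour it under chi-square. These ranges rest on exponential times, follow-up to 72 h, no losses, and BM by 72 h standing in for the rate.

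The point should not be read as a finding that the trial is underpowered. Log-rank and chi-square power exceed 90% at 39 and at 43 per arm. Nor is power adequate on every reading: Fisher at 39 per arm gives 88.7%, slightly under the planned 90%. The latitude left by the undefined POI condition remains unmeasured.

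**What to change.** Before unblinding:

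1. Rewrite Section 4.7.1 so that the single primary endpoint is time from end of surgery to first BM, compared by the log-rank test in the Section 5 modified intent-to-treat population. State one censoring time for patients without a BM. The 72 h used above is an assumption of this review.
2. Remove the POI condition from the primary criterion.
3. Label the rate of BM within 3 days as supportive or secondary, in the same population.
4. Reconcile the success/failure sentence in Section 4.8 with the Section 5 population.

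The cost is protocol and SAP wording, with no extra patients or visits. The downside is that the day-3 rate can no longer serve as an alternative primary result.

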4.7.2 Secondary Measure of Effectiveness

Secondary measures of effectiveness will be determined by the comparative average time to discharge eligibility and/or discharge in hours for the MNTX group versus placebo.

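### The plan does not secure discharge times after unenrolment or withdrawal, so the secondary average can omit ileus-related long stays; *and/or* leaves open that either endpoint carries the claim

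*Combined protocol and SAP*

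**What the plan says.** Section 3.2 lists time to discharge and time to discharge eligibility, both in hours, as two secondary outcomes joined by *and*. Section 4.7.2, under the Success Criteria heading, states the criterion as the "comparative average time to discharge eligibility and/or discharge in hours for the MNTX group versus placebo".

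Section 5 defines a "modified intent-to-treat population including all subjects randomly assigned and having received at least one dose of study drug". It gives Kaplan-Meier estimation to time of first BM, to be "compared between treatment groups using the log-rank test". For the secondary endpoints it gives only the 0.05 "level of significance without adjustment for multiple comparisons". It names no test, summary statistic, censoring rule or missing-data rule for them.

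Two routes lead out of the study. Under Section 4.3, if a treating physician prescribes off-label MNTX for ileus, "the subject will be unenrolled from the study". Under Section 4.8, subjects with a severe concurrent illness are withdrawn: "Such a withdrawal will not be counted for the purposes of determining success or failure". Neither section says whether discharge times are still recorded. The document does not define discharge eligibility.

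**The concern.** Both secondary outcomes are times to an event, and the only description of how to summarise them is an average. An average has no place for a subject whose event time was not observed. Unenrolment under Section 4.3 follows treatment for ileus, so the subjects at risk of having no recorded time are plausibly those with long stays. If they are left out, an arm's stay looks shorter than it was. The comparison is then biased to the extent that losses differ between arms. Losses concentrated in placebo would hide a real benefit; losses concentrated in the MNTX arm would flatter the drug.

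Separately, *and/or* in a success criterion leaves open that a favourable result on either endpoint supports the secondary claim, with each tested at 0.05.

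**Working it through.** **1. What the plan's own figures cover.** The only sample-size statement is for the primary outcome: 43 per group, "90% power; alpha = 0.05", with 50% versus 85% having a first BM by day three and 10% loss. It can be approximately reproduced with Freedman's log-rank formula, two-sided:

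- HR = ln(0.15)/ln(0.50) = 2.74
- events = (1.960 + 1.282)² × [(2.74 + 1)/(2.74 − 1)]², about 49
- 49/0.675 = 72.6, so 73 patients or 37 per arm
- 37/0.90 = 41.1, so 42 per arm against the stated 43

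The documents give no SD, effect size, distribution or power for discharge. Everything below on stay times is an assumption.

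**2. Effect of losing long stays on one arm.** Assume lognormal stays with median 84 h and log-SD 0.5.

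- Full mean = 84 × exp(0.5²/2) = 95.2 h.
- With d = ln(96/84)/0.5 = 0.267, the mean of stays over 96 h is 95.2 × Φ(0.5 − 0.267)/[1 − Φ(0.267)] = 95.2 × 0.592/0.395, about 142.8 h.
- If a share k of the arm is lost, all from stays over 96 h, the mean of the rest is (95.2 − 142.8k)/(1 − k).
- The median of the rest is 84 × exp(0.5 × Φ⁻¹[0.5(1 − k)]).

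| Share lost | Mean (h) | Median (h) |
|---|---|---|
| 0% | 95.2 | 84.0 |
| 5% | 92.7 | 81.4 |
| 10% | 89.9 | 78.9 |
| 15% | 86.8 | 76.4 |

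The median falls by a similar amount, so changing the summary does not by itself remove the bias.

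**3. Effect on the comparison.** This was simulated with lognormal stays, no true effect, 43 per arm, and 10–15% of one arm lost from stays over 96 h.

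| Handling | False-positive rate (nominal 5%) |
|---|---|
| Lost subjects dropped, t-test | 6–16% |
| Lost subjects censored at 72 h, log-rank | 6–13% |
| Everyone followed to discharge, either test | about 5% |

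Censoring helps but does not cure the problem, because the reason for censoring is related to the outcome. Follow-up to discharge does cure it.

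**4. Either endpoint counts.** For two independent tests at 0.05, the chance of at least one false positive is 1 − 0.95² = 0.0975. For correlated endpoints (bivariate normal, two-sided) it is:

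| Assumed correlation | 0 | 0.5 | 0.8 | 0.9 | 0.95 |
|---|---|---|---|---|---|
| At least one false positive | 0.0975 | 0.091 | 0.078 | 0.070 | 0.065 |

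Testing in a fixed order holds it at 0.05.

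**5. Is a comparison of means weak here?** This was simulated with 39 per arm (43 × 0.9 = 38.7), lognormal stays and a shift of 0.65 SD on the log scale.

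| Log-SD | Welch t | Mann-Whitney | Log-rank |
|---|---|---|---|
| 0.3 | 0.79 | 0.78 | 0.72 |
| 0.5 | 0.76 | 0.79 | 0.74 |
| 0.7 | 0.71 | 0.78 | 0.73 |
| 1.0 | 0.63 | 0.79 | 0.75 |

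Means lose clearly only under strong skew. At log-SD 0.3 to 0.5 the t-test is no worse than log-rank.

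**The case against.** The strongest reply is that the plan is silent rather than wrong. Section 4.3 does not say that discharge times stop being collected, and the Section 5 population keeps every randomised and dosed subject. The exclusion in Section 4.8 refers to success or failure, and only Section 4.7.1 defines a subject-level success, in terms of BM. A reader might infer that unenrolled subjects certainly have no discharge time; the documents do not say so. What stands is that nothing requires the times to be collected, and being unenrolled would ordinarily be read as the end of data collection.

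A reader might also infer that the plan commits to a low-power t-test dominated by outliers. It names no test, and it gives no stay distribution from which a power loss could be shown. The 39 per arm used above borrows a 10% loss rate set for the primary outcome, which need not apply to an in-hospital event. That part of the objection stands in full.

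On multiplicity, Section 5 openly declines adjustment, so its 0.05 applies per endpoint and a higher family-wise rate breaches no stated claim. Section 3.2 joins the outcomes with *and*, and Section 4.7.2 speaks of measures in the plural. That either endpoint suffices is one possible reading of *and/or*, not a stated rule. The ambiguity remains because the phrase sits in a success criterion.

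**Conclusion.** The point holds in a limited form. The secondary analysis is under-specified, and as written it allows ileus-related long stays to drop out of an average. In the assumed cases, losing 5–15% of an arm from stays over 96 h shortens its mean by about 2.5 to 8.4 h (95.2 less 92.7, and 95.2 less 86.8). One-sided losses of 10–15% raise the false-positive rate to 6–16% if subjects are dropped, against about 5% with full follow-up. These figures rest on an assumed lognormal shape, median, spread and loss share. The direction of bias in the trial cannot be known in advance.

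If either endpoint may carry the claim, the chance of at least one false positive is about 7% to 9.8% for assumed correlations from 0.9 down to 0. Deleting *and/or* alone would not change that, because two unadjusted tests would remain.

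The documents do not show a general power advantage of log-rank over a comparison of means; with mild skew the two perform about equally. The effect is confined to the secondary endpoints.

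**What to change.** 1. In Sections 4.3, 4.8 and 5, state that time to discharge and time to discharge eligibility continue to be recorded after unenrolment or withdrawal from treatment, unless consent to data collection is withdrawn. State that all randomised and dosed subjects are analysed in their assigned group. Censor only where no discharge time can be obtained, and note that such censoring may be informative.
2. In Section 4.7.2, replace the comparative average with Kaplan-Meier medians with 95% CI and the log-rank test for each endpoint, and repeat this in Section 5. The reason is consistency with the primary endpoint and a defined place for unobserved times, not greater power. Mean hours may be reported descriptively.
3. Replace *and/or* with two separately reported endpoints. If a single secondary claim is wanted, name time to discharge as the first endpoint tested and test discharge eligibility only after it. Time to discharge is the natural first choice because discharge eligibility is not defined in the document; the plan should supply that definition.

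The cost is protocol and SAP wording plus a little data retention after unenrolment. Mean hours saved becomes a descriptive figure.

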4.7.3 Tertiary Measure of Effectiveness

Tertiary measures of effectiveness will include the effect of MNTX on the amount of daily narcotics administered (in milli-equivalents) during the first 4 post-operative days or up to hospital discharge.

4.8 Subject Withdrawal

It is recognized that the subject's participation in this trial is entirely voluntary, and that she/he may refuse to participate and may withdraw from participation at any time without jeopardy to any future medical care. It is also recognized that the investigator, at his/her discretion, may withdraw a subject from this study based upon his/her professional judgment.

Other Conditions for Withdrawal:

Any subject who develops a severe concurrent medical illness during the trial should be withdrawn. This type of illness is defined as any illness that would hinder the subject's ability to return for scheduled follow-up appointments. Such a withdrawal will not be counted for the purposes of determining success or failure.

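### Section 4.8 takes illness withdrawals out of the day-3 success rate although Section 5 keeps every dosed subject, and Section 4.3 unenrols subjects given off-label methylnaltrexone with no rule for their bowel-movement outcome

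*Combined protocol and SAP*

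**What the plan says.** Section 5 bases efficacy analyses on a "modified intent-to-treat population including all subjects randomly assigned and having received at least one dose of study drug" and makes no exception for withdrawals. Under Section 4.3 the first dose of MNTX "or placebo prior to surgery in the pre-operative holding area" is given, so a subject is in this modified intent-to-treat (mITT) set before the operation begins.

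Section 4.7.1 defines success: "A subject will be considered a success if a BM is achieved within 3 days of surgery". It takes as its primary measure the "comparative rate of patients achieving BM and evading POI in the MNTX group versus placebo", where POI is post-operative ileus. Sections 3.2 and 5 instead name time to first BM as primary, and Section 5 analyses it by Kaplan-Meier and log-rank test.

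Two rules act on subjects after dosing:

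- **Severe concurrent illness (Section 4.8).** The subject should be withdrawn, and "Such a withdrawal will not be counted for the purposes of determining success or failure". The illness is one that would hinder the subject's "ability to return for scheduled follow-up appointments".
- **Off-label MNTX (Section 4.3).** If a treating physician prescribes it "for the management of post-operative ileus, the subject will be unenrolled from the study". Nothing is said about that subject's BM outcome.

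**The concern.** The first rule conflicts with the mITT definition as far as the success rate is concerned. Section 5 keeps a dosed subject who later falls ill, and Section 4.8 does not count that subject. The ground for leaving the subject out is unrelated to whether the day-3 outcome was seen.

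The second rule leaves a gap. Section 5, as worded, keeps the unenrolled subject in the mITT set. No section says whether that subject is a failure, is censored, or is still followed for a first BM. The trigger is treatment for ileus, the condition that the Section 4.7.1 measure asks subjects to evade, so the subjects affected are unlikely to be a random sample.

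Two analysts could therefore build different day-3 rates from the same protocol, and recorded outcomes could be set aside after randomisation and dosing.

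**Working it through.** **1. The sections side by side**

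| Dosed subject | In the mITT set (Section 5)? | Counted in the day-3 rate? | BM outcome rule |
|---|---|---|---|
| Withdrawn for severe illness | Yes | No (Section 4.8) | Left out, even if known |
| Prescribed off-label MNTX for ileus | Yes, by its wording | Not stated | None |

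The outcome is settled by day 3. Section 4.3 says that medications, pain and adverse events "will be reviewed daily for up to 96 hours following surgery and at 30 days post-operatively", and the schedule in Section 4.4 has no visit between day 3 and day 30. After the daily in-stay reviews, the only scheduled contact is thus at 30 days. A subject with a BM on day 2 and a severe illness on day 10 would meet the Section 4.8 wording and lose a known success.

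**2. The plan's own figure**

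Inputs (Sections 3.2 and 4.2): 50% vs 85% with a BM by day 3, 90% power, alpha 0.05 (two-sided assumed), 10% loss, 43 per arm.

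Pooled two-proportion formula: n = [1.960√(2 × 0.675 × 0.325) + 1.282√(0.5 × 0.5 + 0.85 × 0.15)]² / 0.35² = 35.5, so 36, and 36/0.9 = 40. With continuity correction the result is 42, and 42/0.9 gives 47. Neither gives 43, but nothing below depends on that. After 10% loss, 43 × 0.9 = 38.7, so about 39 per arm.

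**3. Illustration: 4 day-3 failures left out (an assumed count)**

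Expected successes are 43 × 0.50 = 21.5 and 43 × 0.85 = 36.55.

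| Left out of | Placebo | MNTX | Difference |
|---|---|---|---|
| Neither arm | 21.5/43 = 50.0% | 36.55/43 = 85.0% | 35.0 points |
| Placebo only | 21.5/39 = 55.1% | 85.0% | 29.9 points |
| MNTX only | 50.0% | 36.55/39 = 93.7% | 43.7 points |
| Both arms | 55.1% | 93.7% | 38.6 points |

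**4. The same share f of failures left out of both arms**

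The rate becomes p / [p + (1 − p)(1 − f)]. Section 2.1 cites a POI incidence of 0.6 to 16.7%. As shares of the 50% placebo failures these are 0.6/50 = 1.2% and 16.7/50 = 33%. The range assumes that every POI case is a day-3 failure and receives off-label MNTX, which the documents do not say. At f = 1/3 the rates are 0.5/0.8333 = 60.0% and 0.85/0.95 = 89.5%.

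Power = Φ{[Δ − 1.960√(p̄(1 − p̄)(1/n₁ + 1/n₂))] / √(p₁(1 − p₁)/n₁ + p₂(1 − p₂)/n₂)}, where Δ is the difference in rates, p̄ the pooled rate, and each n is reduced by the subjects left out.

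| f | Difference | Power from 43 per arm | Power from 39 per arm |
|---|---|---|---|
| 0 | 35.0 | 94.8% | 92.6% |
| 1.2% | 34.9 | 94.6% | 92.3% |
| 10% | 33.7 | 93.0% | 90.4% |
| 20% | 32.1 | 90.6% | 87.6% |
| 33% | 29.5 | 86.0% | 82.4% |

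**5. Illness withdrawals**

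If illness is unrelated to outcome, the rates are unbiased. Leaving out 1 / 2 / 4 per arm gives power of 94.3 / 93.8 / 92.6% from 43, or 91.9 / 91.2 / 89.6% from 39. With 2 of 39 per arm left out, the rates read 52.7% vs 89.6% if all were failures and 47.3% vs 84.2% if all were successes. The difference is 36.9 points either way.

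**6. The planned log-rank test, if these subjects were censored**

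Simulation: 39 per arm, exponential first-BM times set to 50% and 85% by 72 h, BM observation to 96 h (assumed), censoring at 36, 48 or 60 h, f from 1.2 to 33%, 3,000 replicates per case. Power is 94.0–97.7%, against 97.6% with none censored (Monte Carlo error about 0.3 to 0.4 points). The placebo day-3 Kaplan-Meier estimate stays at 49.9–50.2% if those censored are a random share of subjects still without a BM. If all of them would have had no BM by 72 h, the extreme case, it reads 50.6–51.8 / 51.4–53.4 / 52.5–56.6% at f = 10 / 20 / 33%.

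**The case against.** **Section 4.8 may mean less.** The sentence could say only that the act of withdrawing is not itself scored, leaving an earlier BM to count. It could also be a deliberate exception to Section 5. Either is possible. The first is the less natural reading, because success is exactly what Section 4.7.1 defines per subject. The second is nowhere stated in Section 5. The text needs reconciling in any case.

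**The day-3 rate has no planned test.** This stands. Section 5 specifies the log-rank test only, so the two-proportion powers above belong to a test that the plan does not specify. The rate still matters: Section 4.7.1 calls it the primary measure, and the sample size rests on day-3 proportions.

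**Attrition may be counted twice.** This also stands. These withdrawals may already sit inside the 10% allowance, which is why results are shown from both 43 and 39 per arm. From 43, only f = 33% takes power below 90%.

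**The upper end of f is not an estimate.** Agreed. The cited 16.7% is POI incidence, not off-label prescribing, and every patient already receives a bowel routine.

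**Unenrolment need not end data collection.** Correct. Consent terms, which are not in the documents reviewed, may cover it. The protocol and SAP do not say.

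**Conclusion.** The concern holds for the day-3 success rate. Section 4.8, read plainly, conflicts with the mITT definition and can discard an observed outcome. Section 4.3 removes subjects on an ileus-linked trigger with no outcome rule.

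The size is unknown and may be small, because the documents give no frequency for either event. The shift to 29.9 or 43.7 points rests on an assumed 4 failures lost from one arm. The power figures show sensitivity to attrition assumptions and do not forecast this trial's power.

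The documents do not support three stronger readings that a reader might infer:

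- **That the primary log-rank analysis is compromised.** If these subjects are censored, its power is almost unchanged. The Kaplan-Meier estimate is biased upward only to the extent that those censored have a worse outlook than others still at risk. What is missing is a statement that they are censored.
- **That the rules favour MNTX.** The direction depends on which arm loses subjects and on their outcomes. Losing an equal share of failures from both arms shrinks the difference.
- **That every affected subject is a failure.** A first BM may already be recorded before the illness or the off-label prescription.

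**What to change.** Reconcile Sections 4.3, 4.8 and 5 before unblinding:

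1. Remove the Section 4.8 sentence on success and failure for efficacy purposes.
2. State that all dosed subjects stay in the mITT analysis after illness withdrawal or off-label MNTX unenrolment.
3. State that first-BM data continue to be collected unless consent to data collection is withdrawn, and that a first BM recorded before the event counts as observed.
4. Define the end of BM observation. The 96-hour window in Section 4.3 covers medications, pain and adverse events and does not name BMs.
5. Pre-specify one handling for each case with no BM before the event:
   - *Illness or other withdrawal with later data missing:* for example, censored at the last BM assessment in the log-rank analysis, with the day-3 rate taken from Kaplan-Meier.
   - *Off-label MNTX:* for example, not a success for the day-3 rate, and at risk without event to the end of BM observation.
6. Add a sensitivity analysis using the alternative handling and actual first-BM times. It is needed because the choice for off-label use is one of several that could be defended.

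The cost is a few sentences and a few extra BM records. Success rates may read slightly lower. No change to prescribing, dosing or the decision to withdraw is proposed.
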